3.1 Project population, inclusion and exclusion criteria

The project population consists of healthy adults over the age of 35 years, regardless of gender or ethnicity, who are willing and able to give their informed consent to participate in the study. The total number of participants will be 60. The choice of participants over 35 years is because in younger individuals collagen is not yet depleted or only to a small extent ⁶. To ensure gender balance in the recruitment, our inclusion criteria are gender-neutral, gender-neutral language is used in all study materials and advertisements and we will engage in diverse recruitment to target a broad population.

Participants fulfilling the following inclusion criteria are eligible to participate in the study:

- Age 35 or older, regardless of gender, ethnicity or socioeconomic background
- Voluntarily purchasing the collagen activator (from Avea) for 6 months with the intend to take it on a daily basis
- Willing to fill out the questionnaires on a monthly basis.
- Willing to participate in all measurements part of the study (Skin tests & saliva samples)
- Able to appear at the baseline, 1 and 3 month follow up visits at the Dermatology clinic "Hautwerk" in Zürich.

If any of the following exclusion criteria are present, the participant will be excluded from the study:

- Underlying health conditions leading to regular intake of medication, including:
 - o Diabetes
 - o Hypertension (high blood pressure)
 - o Cardiovascular disease
 - o Asthma
 - o Chronic obstructive pulmonary disease (COPD)
 - o Arthritis
 - o Depression
 - o Anxiety
 - o Epilepsy
 - o Cancer
 - o Thyroid disorders
 - o Autoimmune diseases such as lupus or multiple sclerosis
 - o Chronic kidney disease
 - o Liver disease
 - o HIV/AIDS
 - o Chronic pain conditions such as fibromyalgia or chronic migraine.
 - 0 ...

- Chronic skin condition, independent of treatment, including:
 - o Acne
 - o Eczema
 - o Psoriasis
 - o Rosacea
 - o Skin cancer
 - ο.
- Intake of any collagen supplements 3 months prior to the screening date
- Smoking at time of recruitment or smoking up to 5 years prior to recruitment
- Pregnancy or lactating at the time of recruitment or planning to get pregnant in the following 6 months
- Insufficient knowledge of the German or English language
- Unable to give consent
- Unable to follow the procedures that are part of the study

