Aging also affects elastin, another crucial protein in the skin. Exposure to UV radiation enhances elastin degradation, while reduced synthesis by fibroblasts leads to decreased skin elasticity. Hyaluronic acid, which plays a vital role in skin hydration, experiences a reduction in synthesis, leading to decreased skin hydration⁷.

In conclusion, skin aging is a complex process involving changes in the epidermis, dermal-epidermal junction, and dermis. The signs of skin aging, including wrinkles, age spots, reduced elasticity, reduced hydration, and increased transepidermal water loss, are the result of these changes. Understanding the molecular and cellular mechanisms underlying skin aging can help in the development of effective anti-ageing strategies 57.

Epigenetic methylation clocks are emerging as a promising biomarker of biological age. DNA methylation is a chemical modification of DNA that regulates gene expression and plays a critical role in development and aging. Methylation patterns change over time, and researchers have developed epigenetic clocks based on DNA methylation patterns to estimate biological age ⁸⁻¹².

Accelerated epigenetic clocks, which are associated with older biological age, have been linked to several health outcomes. Studies have shown that accelerated epigenetic clocks are associated with mortality, cardiovascular disease, cancer, diabetes, and higher BMI ¹³⁻¹⁷. Intervention studies have used epigenetic clocks to show a reduction in biological age. For example, diet and lifestyle interventions have been shown to reduce biological age, as measured by epigenetic clocks ¹³⁻²⁰. Additionally, supplementation with alpha-ketoglutarate has been shown to decrease biological age ²¹. These findings suggest that epigenetic clocks may be useful in evaluating the efficacy of interventions aimed at improving health and longevity. Our trial provides an opportunity to further establish the correlation between epigenetic clocks and relevant health measures. By measuring DNA methylation patterns and biological age in our participants, we can evaluate the relationship between epigenetic clocks and health outcomes, in our case multiple measures of skin aging. These findings may provide insights into the mechanisms underlying aging and identify new targets for interventions aimed at improving health and longevity.

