2.1 Hypothesis and primary objective

Primary objective: Intake of the collagen activator from Avea for 6 months will result in a significant decrease in biological age compared to the baseline.

Secondary objective: Intake of the collagen activator from Avea will lead to a significant improvement in skin quality and texture, including increased hydration, elasticity, and reduction in wrinkles, pigmentation, texture, UV-spots, pores, redness, and porphyrins after 3 months compared to baseline.

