2.3 Project design

The study is a human research study in which customers that are taking the collagen activator from Avea are observed for six months. The trial is in the form of a post marketing surveillance observational trial since the product has already been approved and is sold on the market. All participants are voluntarily taking the collagen activator. There is no blinding, randomization or placebo control that is taking place in the trial. The results are compared individually for each participant after the follow ups from their baseline measurements.

- The trial exposure is the Collagen activator from Avea
 - Potential participants are contacted after purchasing the collagen activator for 6 months via Avea's online shop. After successful recruitment they undergo the baseline assessment. They are instructed to only start taking the collagen activator once the baseline assessment is completed.
 - o Daily oral intake of 1 package of 11.5g diluted in water over six months, taken in the morning
- Saliva samples are taken twice (time points 0 and +6 months) to determine biological age via epigenetic methylation clock (Trume labs are the test providers and analysers)
- Skin analysis takes place at time points 0, +1 and +3 months to determine skin quality. This includes measurements of hydration, elasticity, skin thickness and density, as well as pigmentation, wrinkles, texture, UV-spots, pores, redness and porphyrins.
- Skin tests used for this are the corneometer, cutometer, ultrascan and Visia scan.
- Every month the participants receive a questionnaire regarding recent subjective changes, adverse reactions and adherence

The individual duration expected for each patient from the recruitment process onwards is about 6-7 months

- The goal is to recruit 60 healthy participants that are older than 35 years and are voluntarily taking the collagen activator for 6 months
- 2-3 weeks from being recruited to receiving a date for the baseline measurements
- Day 1 being the day of the baseline measurements
- Follow ups for the skin measurements take place +1 and +3 months from day 1
- Follow up for the saliva test takes place +6 months from day 1

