- 3. Ultrascan: Ultrascan is a non-invasive device that uses high-frequency ultrasound waves (22 Mhz) to measure the thickness and density of the skin. The device works by emitting ultrasound waves into the skin, which bounce back and are recorded by the device. The time it takes for the ultrasound waves to bounce back is used to calculate the thickness of the skin. This measurement is used to assess the overall health of the skin and collagen content can be read out by it.
- 4. Visia scan: Visia scan is a non-invasive imaging system that captures high-resolution images of the skin's surface. The device uses different types of light, such as UV, polarized, and non-polarized light, to capture images of the skin at different depths. The images are then analyzed to assess various skin conditions, including pigmentation, wrinkles, texture, UV-spots, pores, redness, and porphyrins. This measurement is used to assess the overall health and quality of the skin.

At the time points +1, +2, +3, +4 +5 and +6 months of the study duration, a short online questionnaire will be sent to all participants via email, with a secure link to the REDcap online form. It will contain questions about the product intake (how many days of the months), the health status (any changes, physical or mental illness, adverse reactions), important lifestyle changes, and if the participants are still willing to continue with the study. There will also be the possibility for the participants to reach out to a medical professional or to schedule a visit.

At the timepoints +1 and +3, follow-up visits at the Dermatology clinic Hautwerk will be scheduled (time frame +/- 1 week of the +1 and +3 months time point respectively). The visit will contain the same procedures as the visit at time point 0, minus the saliva sample. The medical professional will again first check the completion of the questionnaire and assist if necessary, then take the skin scan (Visia analysis system), and the tests with the corneometer, cutometer and ultrascan. The participants have then time to rest to make sure there are no adverse reactions to any of the procedures. At time point +3, the participant will be provided with the saliva collection kit for timepoint +6 months. Each visit will be recorded by the medical professional. The total visit should take between 30 to 60 minutes.

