The decision to conduct these analyses in the USA is rooted in a combination of scientific precedent and practical considerations. In a previous study²¹ that utilized the same company and testing method for analyzing biological age, remarkable outcomes were observed. This study indicated an average reduction of 8 years in biological age after an average of 7 months, and notably, the supplement used also contained alpha-ketoglutarate. Given this promising precedent, we aim to replicate these impressive results in our current study, maintaining consistency with the methods that led to such a meaningful outcome previously.

Furthermore, we've also considered the availability of alternative options within Switzerland. While ensuring local analysis is desirable, unfortunately, there are no local competitors who offer similar analyses at a cost comparable to the arrangement we have with our current US-based partner. Budget constraints are a significant consideration for our study, and partnering with the US-based company allows us to achieve comprehensive and high-quality analyses without compromising the study's financial scope.

Swiss dataprotection regulations upheld in the US:

- All saliva samples sent to the US laboratory are encoded using encryption protocols, which adhere to both Swiss Federal Data Protection Act (FADP) and US data security standards. This step ensures that the genetic material remains secure and unreadable during transmission and analysis, minimizing the risk of unauthorized access.
- As the scope of analysis is limited to only 9 short gene sequences directly relevant to determining biological age, this focused approach ensures that only the necessary genetic information is utilized, in alignment with Swiss data protection principles of data minimization. Once this analysis is completed and the biological age is determined, the genetic information used for this specific purpose is promptly deleted. This precautionary measure adheres to both Swiss and US regulations and minimizes the retention of sensitive information to what is strictly essential.
- Throughout the entire process, the US laboratory conducting the analysis does not have access to any identifying information linked to the samples. This includes personal details of the participants or any contextual information. The encrypted data ensures that the laboratory lacks the capacity to link the samples to specific individuals, thereby preserving the anonymity of participants.

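### Section 3.1 excludes recent users of collagen supplements but not of alpha-ketoglutarate, which the protocol presents as lowering the primary endpoint, and other supplements are never named among the confounders to be collected

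*Protocol*

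**What the plan says.** Section 2.1 sets the primary objective: "Intake of the collagen activator from Avea for 6 months will result in a significant decrease in biological age compared to the baseline". Section 2.3 says of the design: "There is no blinding, randomization or placebo control that is taking place in the trial". Each participant is compared with their own baseline.

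The background (section 1) states that "supplementation with alpha-ketoglutarate has been shown to decrease biological age", and section 2.2 lists AKG again among the interventions supporting the primary endpoint. Section 7.3 describes a precedent that used the same test provider: "This study indicated an average reduction of 8 years in biological age after an average of 7 months". It adds that "notably, the supplement used also contained alpha-ketoglutarate" and says the sponsor hopes to replicate the result.

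On supplements, section 3.1 has one exclusion: "Intake of any collagen supplements 3 months prior to the screening date". Neither list in 3.1 mentions AKG, other supplements, or supplements started during follow-up.

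On data capture, section 3.3 says of the monthly form: "It will contain questions about the product intake (how many days of the months". It goes on to health status, important lifestyle changes and willingness to continue. The same section promises questions on potential confounders, with illness and major behaviour changes as examples. The primary model in section 4.1 has two covariates, chronological age and sex.

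**The concern.** The collagen criterion shows that the sponsor accepts that recent supplement use can spoil a baseline. Collagen is the exposure the background links to the skin measurements, which are secondary endpoints. AKG is the exposure it links to biological age, the primary endpoint, and no criterion covers it.

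In an uncontrolled before-after study, attributing the change to the product depends heavily on a clean baseline and on stable co-exposures. Two errors are possible, in opposite directions:

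- A participant already on AKG may have a baseline that is already shifted, so the change measured on the product may be smaller than in a new user.
- A participant who starts another age-active supplement during the six months may show a fall that is then credited to the product.

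If the exposure is not recorded, no later analysis can separate either effect from that of the product.

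**Working it through.** **Step 1. Which exposures does each provision cover?**

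| Provision | Study product before baseline | Other collagen before baseline | AKG from another source before baseline | Other supplement started during follow-up |
|---|---|---|---|---|
| 3.1 collagen exclusion, 3 months | limits it, if the product counts as a collagen supplement | yes | no | no |
| 3.2 recruitment after first purchase | yes | no | no | no |
| 2.3 start only after baseline | yes | no | no | no |
| 3.1 exclusion for regular medication | no | no | no (concerns health conditions) | no |
| 3.3 questionnaires | not named | not named | not named | not named |
| 4.1 primary model | no term | no term | no term | no term |

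The gap lies in the last two columns. Only the questionnaires could fill it, and their description is open-ended but does not name supplements.

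**Step 2. Is AKG in the study product?** No composition is given. Section 7.3 says the precedent supplement *also* contained AKG, which implies that the study product does. The point about supplements started during follow-up does not depend on this inference.

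**Step 3. Can the bias be sized?** That would need the share of participants using such supplements, their effect on this test and the standard deviation (SD) of the within-person change. The documents give no co-use rate and no SD, and the only effect figure belongs to a multi-ingredient formulation. What follows illustrates sensitivity and is not an estimate.

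The evaluable sample comes from section 4.1: one-sided 0.05, power 0.8, effect size 0.5, n = 50. This reproduces as the per-group size of a two-sample comparison: 2 × (1.645 + 0.842)² / 0.5² = 49.5, so 50. Then 50/0.85 = 58.8, so 59, and 50/0.80 = 62.5, so 63. A one-sided paired t-test at the same settings needs 27 (26.1 before rounding up). That is a separate matter, but it explains why power starts well above 80% below.

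Assume 50 completers, a one-sided paired t-test at 0.05 and a change SD of 1. With effective standardised change d, power is 1 − F(t₀.₉₅,₄₉), where F is the noncentral t distribution with 49 degrees of freedom and noncentrality d√50.

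*Dilution.* Assume that a share f are prior AKG users who show no further change and that the true effect in the others is 0.5. Then d = 0.5(1 − f) / √(1 + 0.25 f(1 − f)).

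| f | d | power |
|---|---|---|
| 0 | 0.500 | 96.7% |
| 10% | 0.445 | 92.8% |
| 20% | 0.392 | 86.2% |
| 30% | 0.341 | 76.9% |
| 50% | 0.243 | 51.8% |

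*Inflation.* Assume that the product has no effect and that a share f start another age-active supplement with effect D (in SD units). Then d = fD / √(1 + f(1 − f)D²), and the chance of a significant fall is:

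| f | D = 0.5 | D = 1.0 |
|---|---|---|
| 0 | 5% | 5% |
| 5% | 7.1% | 9.6% |
| 10% | 9.7% | 16.4% |
| 20% | 16.8% | 36.3% |
| 30% | 26.6% | 60.1% |

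Dilution is tolerable at modest shares. Inflation can take the error rate well above 5% if co-use is common and effective. Neither condition can be judged from the documents.

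**The case against.** Several counter-arguments have force.

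- **Confounder questions are promised.** The examples in section 3.3 are not exhaustive, and a baseline medical questionnaire is completed or checked with a doctor. The forms themselves are not part of the protocol text. A reader might infer that the sponsor will be blind to other supplements. The text supports only that supplements are not named, so their capture is not assured.
- **Earlier exposure is partly controlled.** A reader might infer that the primary endpoint has no wash-out at all. That goes too far: first-time purchase, starting after baseline and the collagen exclusion limit prior use of the study product. Section 3.1 also excludes recent smokers and people on regular medication for health conditions. What is missing is a limit on AKG from other sources.
- **AKG content is an inference.** It rests on one word in a paragraph that justifies the choice of laboratory. The inference is reasonable, but the content is not stated.
- **The 8-year figure does not size the bias.** It is tempting to multiply it by a share of participants who start AKG elsewhere. The title of reference 21 describes a formulation of AKG with vitamins, so the figure does not isolate AKG. If the study product contains AKG, it is also inconsistent to assume that AKG works from another brand and does nothing here.
- **The study observes ordinary customers.** Section 2.3 calls it post-marketing observation and section 6.1 stresses generalisability, so leaving other supplements unrestricted is defensible. But the sponsor already restricts collagen, and recording supplements costs no generalisability.

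These arguments narrow the point and remove any claim about its size. They do not explain why the exposure linked to the secondary endpoints is screened while the one linked to the primary endpoint is not.

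**Conclusion.** The concern holds in this limited form: the supplement criterion does not cover the agent that the protocol itself presents as lowering biological age, and other supplements are not named among the data to be collected. In a single-arm before-after comparison adjusted only for age and sex, this leaves a bias that could go either way and that analysis cannot repair if the exposure goes unrecorded.

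Its size is unknown. The power and error rates shown rest on assumed co-use shares, assumed effects and a change SD of 1, and illustrate sensitivity only. The dilution argument for AKG also relies on the implied, unstated presence of AKG in the product. The documents do not show that any participant uses AKG from another source. The change should be made before enrolment because it is cheap and exposure history is hard to recover afterwards.

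**What to change.** 1. In section 3.1, extend the existing exclusion to intake of any collagen or alpha-ketoglutarate-containing supplement, with the same 3-month look-back. The documents give no carry-over time for AKG on this test, so the 3 months is taken over for consistency and the protocol should say so.
2. In section 3.3, name other supplements among the confounders collected: those taken at baseline, and those started or stopped in each monthly questionnaire.
3. In section 4.1, state that participants who start another supplement stay in the primary analysis, and that this analysis is repeated without them as a sensitivity analysis.
4. State in the protocol whether the study product contains AKG, so that the rationale no longer depends on inference.

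The cost is an amendment, a slightly smaller pool of eligible customers and one or two extra questionnaire items. The planned sample size need not change on this account.

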3.2 Recruitment, screening and informed consent procedure

Recruitment will be conducted through advertising the study to Avea customers after they have bought the collagen activator in the Avea online shop for the first time. The advertisement will be uploaded in BASEC.

Potential participants are Avea customers, therefore the Avea team has access to their email addresses. The study advertisement is sent to the email address under which the order was placed. The first round of pre-selection will be done by the potential participants themselves by going through the study advertisement and the description of the trial. If a person decides they are interested in participating, they can fill out the inclusion and exclusion guestionnaire which is attached to the advertisement (via a link to a google form). In this form they enter their email address. For questions they can reach out via email to the person in charge of recruitment at Avea. The results of the google form are only visible to the Avea team member in charge of recruitment. Once that person has decided if a person is eligible to participate according to the criteria defined in section 3.1 (if uncertain the decision is made together with [name]), the answers of the google form are deleted immediately and the email address is transferred to RedCap. From then on they are considered as participants and all information is securely stored and encrypted in RedCap. Via RedCap they then receive the detailed study information. This entails the nature of the study, its purpose, the procedures involved, the expected duration, the potential risks and benefits and any discomfort it may entail. Each subject is informed that the participation in the study is voluntary and that he/she may withdraw from the study at any time and without stating any reason. The withdrawal of consent will not affect his/her subsequent medical assistance and treatment. The subjects are informed that he/she can ask any question, and consult with family members, friends, their treating physicians or other experts before deciding about their participation in the study. Enough time is given to the subjects to make a decision and to give informed consent at all times. The subjects are informed that authorized individuals may examine his/her medical records and how and for which purpose the extracted data will be used.

Together with the detailed study information they receive a booking link from the Hautwerk clinic (only for the study) where they can schedule their first appointment (within the following 3 weeks) if they remain willing to participate. They can schedule a phone call with [name] to clarify any remaining questions (optional they can also reach out to her via email if there are only a few or no questions).

At the first appointment, each subject will once again fill out the inclusion and exclusion questionnaire to confirm their eligibility for the study. [name] will explain again to each subject what it means to be part of the study (see paragraph above), and will fill out the informed consent form with each participant.

The participants should read, understand, and voluntarily agree before signing and dating the informed consent form, and are given a copy of the signed document. The consent form is signed and dated by the participant and the Project leader Frau [name], or her assigned substitute. The signed consent form is retained as part of the investigation records.

No direct payment is given to the study participants. Each person does receive the skin scans and results of the saliva biological age tests after completion of the study free of charge (information only provided after completion of the study and if the participant has not informed us of not wanting to receive this information).

